#### 4.4 Collection and handling of biological samples

The procedures for taking blood samples from the mothers and the babies will follow standard procedures at the investigational sites. The anticipated total amount of blood taken from the mothers during the study period of approximately 5 months until delivery is up to approximately  $10 + 105 + 100 = 215$  mL, please see Table 4, where the total amount of blood taken from the babies will not exceed approximately 20 mL, during their first 3 months of life.

For the babies the target blood volumes for the immunogenicity samples are as follows: 5 mL for cord blood, 2 mL for venous blood and 0.5 mL for heel prick blood. Whenever possible cord blood should be taken, venous blood has second priority followed by heel prick blood.

**Table 4 Number of tests, volumes of blood per test and total volume of blood for mothers**

|                                | Number of tests | Volume of blood per test, mL | Total blood volume, mL |
|--------------------------------|-----------------|------------------------------|------------------------|
| Biochemistry                   | 7               | 10                           | 70                     |
| Haematology                    | 7               | 5                            | 35                     |
| Hep B, Hep C, HIV and syphilis | 1               | 10                           | 10                     |
| Immunogenicity                 | 5               | 20                           | 100                    |
| Total blood volume, mL         |                 |                              | 215                    |

The procedures for taking blood samples from the mothers and the babies, processing, storage, and shipment of biological samples to internal and external laboratories, will, be described in more detail in a study specific laboratory manual.

## 4.5 Laboratories safety and immunogenicity

The safety laboratory tests will be performed at accredited laboratories, and assessments of the results will be in accordance with current normal ranges, and these will be updated during the course of the study, if applicable.

The ELISAs for detection of IgG specific to the four AlpN domains (RibN, AlpCN, Alp1N, Alp2/3N), i.e., the primary and secondary immunogenicity laboratory analysis, will be validated and performed according to good clinical practice for laboratories.

### 4.5.1 Biobanking

Only biological samples, where written informed consent to storage in a biobank (after completion of the laboratory analysis included in the protocol), has been obtained from the study subjects, may be transferred to a biobank. Biobank procedures will be in accordance with applicable general data protection regulations (GDPR).

All biological samples are pseudonymised at all times and are not labelled with information which can be used to reveal the identity of the subject, unless access is obtained to the non-pseudonymised data kept at the trial site under the responsibility of the PI(s).

The biological samples taken for safety laboratory analysis specified in this protocol are destroyed after completed analysis.

For the biological samples taken for the immunogenicity laboratory analysis, remaining sample will be transferred to a biobank, after the laboratory analysis specified in the protocol have been completed, if informed consent has been obtained from the subject. The biological samples in the biobank will be used for future immunological research.

## 4.6 Study population

### 4.6.1 Overall description of study subjects

A total of 270 pregnant women are planned to be randomised. Sixty participants are assigned to Groups 1 to 3 where the 3 different, two-dose vaccination regimens of GBS-NN/NN2 are administered, 60 participants are assigned to a single dose of GBS-NN/NN2 (Group 4) and 30 participants assigned to three doses of placebo (saline) (Group 5).

Pregnant women, over the legally defined age of consent, carrying a normal singleton pregnancy and is at the planned time of the 1st vaccination, will be recruited from antenatal clinics, connected to the investigational sites, if expected to be available for the scheduled clinic visits for the duration of the study, agree to be contacted by telephone during study participation, and are willing to give parental consent for their baby to participate in the study.

Women may also be identified via a mailout according to local arrangements. One way to identify eligible women will be from hospital lists of patients due to attend for antenatal care.

Potential participants may be approached regarding the study at routine antenatal visits where the pregnant women will be informed about the study.

The rationale for including a pregnant study population, is that the GBS-NN/NN2 investigational vaccine is targeted for vaccination of pregnant women, aiming at passive immunization of their babies with the antibodies generated by the mother, to provide protection of the baby against invasive GBS disease during the first three months of life.

Each woman will, after a screening period of up to 2 weeks, be in the study for approximately 18 weeks (4 ½ months) from 22 weeks GA until delivery, followed by an additional 6 month's post-delivery follow-up period, with safety and immunogenicity assessments for mothers and babies, please see Table 1, Table 2 and Table 3. Taking visit windows into account the study duration for each woman is up to approximately 1 year.

### 4.6.2 Inclusion criteria

1. Healthy pregnant woman above the legally defined age of consent at the time of screening
2. Carrying a normal singleton pregnancy, and is at 21+0 to 23+6 weeks GA at the planned time of the 1st vaccination, as established by first/second trimester ultrasound examination.
3. Properly informed about the study and has given written informed consent and parental consent (for her baby) in accordance with ICH GCP and local legislation prior to the first study intervention

4. Grants access to her own and her baby's study related medical records

#### 4.6.3 Exclusion criteria

1. Previous vaccination with an investigational Group B Streptococcus (GBS) Vaccine
2. BMI of <17 or >40 at the time of screening
3. HIV, HBV and/or HCV positive or positive for syphilis
4. Knowingly carrying, at screening, a malformed or genetically abnormal foetus, incl. renal pelvis dilation, single umbilical artery (screening will be undertaken after the ultrasound conducted for the detection of anomalies)
5. Chronic or pregnancy induced hypertension at screening, >1+ protein in urine regardless of blood pressure or 1+ protein in urine and hypertension
6. Experienced a previous stillbirth prior to going into labour
7. Gestational, type 1 or type 2 diabetes
8. Potential placenta previa as per malformation ultrasound scan
9. Rhesus negative and has anti-D antibodies or other potential harmful antibodies
10. Known or suspected allergies to any components of the vaccine including to aluminium or aminoglycoside antibiotics, or an allergic reaction related to a previous vaccination
11. Fever (temperature >37.9°C) on the day of receiving the first dose or an acute infection in the 7 days before the first dose (the first dose can be delayed if gestational age permits)
12. Received systemic steroids in the 6 weeks before the first dose (inhaled and topical steroids are acceptable)
13. Any lesion (including tattoos) at the planned injection site that will impair the assessment of the injection site
14. Received immunosuppressive medication, chemotherapy or radiotherapy in the 24 weeks before the first dose
15. Received blood, blood products, plasma derivatives or any immunoglobulin preparations in the 12 weeks before the first dose
16. Anaemia, haemoglobin (<10 g/dL, 100 g/L, 6.2 mmol/L)
17. Currently breast feeding
18. Received any investigational medicinal product or vaccine in the 12 weeks or 5 half-lives before the first dose
19. Received an approved vaccine within the 4 weeks before the first dose or expects to receive an approved vaccine during the study. Routine vaccinations recommended during pregnancy (e.g., pertussis and influenza) are permitted but every effort should be made to separate routine vaccinations from the trial vaccinations by at least 7 days.

20. Known or suspected immunodeficiency or cancer (leukaemia, lymphoma), or a family history of congenital or hereditary immunodeficiency
21. History or presence of uncontrolled cardiovascular disease, pulmonary, hepatic, gall bladder or biliary tract, renal, haematological, gastrointestinal, endocrine, immunologic, dermatological, neurological, psychiatric, or autoimmune disease
22. History of, or current drug or alcohol abuse
23. In the opinion of the investigator not suitable for inclusion in the study
24. The pregnancy is considered high risk by treating physicians

## 4.7 Discontinuation of subjects and treatment

A subject may be discontinued from therapy (i.e., not receive her second dose), but remain in the study for follow-up, for safety and immunogenicity study endpoints, if applicable, in the opinion of the investigator.

### 4.7.1 Subject discontinuation (individual subject)

A subject is free to leave the study any time without giving a reason, according to the Declaration of Helsinki.

Although a subject is not obliged to provide reason(s) for withdrawing consent, the investigator must make a reasonable effort to ascertain the reason(s), while fully respecting the subject's rights.

If the reasons are obtained, the primary reason for withdrawing consent must be specified in the end-of-study form in the eCRF.

The investigator may withdraw an individual subject from the study in case of an adverse event that, in the opinion of the investigator, precludes any further participation in the study, the primary reason for the investigator's decision, must be specified in the end-of-study form in the eCRF.

### 4.7.2 Treatment discontinuation (individual subject)

Discontinuation of study treatment is not the same as withdrawal from the study. If vaccination is stopped for an individual subject, the subject may stay in the study to perform scheduled assessments, if applicable, in the opinion of the investigator.

A permanent contraindication (stopping rule) is defined as an adverse event experienced by a study subject that leads to the conclusion that no investigational product can be administered to the study subject anymore, i.e., withdrawal from administration of the investigational product.

The investigator must permanently stop vaccination of an individual subject in case of:

- An objective clinical or laboratory parameter change which by the investigator is assessed as severe in intensity AND is judged to be related to the investigational product

- An AE thought to be an allergic reaction to the investigational product, including anaphylaxis, bronchospasm, perioral oedema, extensive rash (>40% body surface), urticaria, generalized petechiae, or erythema multiforme judged to be related to the investigational product
- Temperature >38.9 °C within 72 hours after a vaccination, for no apparent reason
- Any event that in the opinion of the investigator precludes administration of any further investigational product

For solicited local or systemic reactions reported and rated by the subjects in the eDiary, it is at the investigator's discretion to assess if the individual subject should be withdrawn from study treatment, according to the criteria above.

Subjects withdrawn from the study within 6 months after the last product administration, will be contacted at least 6 months after the last product administration for recording of SAEs and AEs of special interest.

A temporary contraindication (pausing rule) is defined as an event experienced by a study subject that leads to the conclusion that no investigational product can be administered to the study subject until the event has resolved.

The investigator must postpone the vaccination of an individual subject in case of:

- Acute infection in the 7 days before the vaccination or treated for acute infection with antipyretics/analgesics in the 24 hours before the vaccination
- Elevated temperature measured prior to the vaccination (> 37.9 °C)

The vaccination is postponed until 7 days after the acute infection has resolved, the antipyretics/analgesics treatment has ceased for 24 hours and/or the temperature is ≤ 37.9 °C.

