## 2 Introduction

### 2.1 Background Group B streptococcus (GBS) infection and disease

*Streptococcus agalactiae*, also referred to as Lancefield's group B Streptococcus (GBS), is a Gram-positive diplococcus that colonizes the gastrointestinal and genital tracts of up to 30% of women. Normally, a commensal it does not cause clinical problems for colonized women. However, in pregnant women who are colonized with GBS there is a significantly higher occurrence of postpartum fever and endometritis compared to women who are not colonised. GBS is the most common causes of life-threatening invasive bacterial infections in neonates and young infants. Infections can result in neonatal sepsis, pneumonia and meningitis, in infants living in diverse regions (Fluegge et al. 2006; Lin et al. 2018; Neto 2008; Rivera et al. 2015), and is associated with significant mortality and morbidity, including long-term neuro-developmental sequelae (Kobayashi et al. 2016). GBS is also associated with disease in adults particularly in the elderly and adults who are immunosuppressed. GBS is also a cause of mastitis and perinatal puerperal infections (Kobayashi et al. 2016; Nuccitelli, Rinaudo, and Maione 2015; Kvist et al. 2008; Pass, Gray, and Dillon 1982; Shet and Ferrieri 2004).

GBS infection in new-borns is usually classified as early-onset disease (EOD), occurring during the first 6 days of life and late-onset disease (LOD) occurring between day 7 to 89 days of life. It is estimated that 60–90% of EOD occurs on the first day of life following in-utero infection (Verani, McGee, and Schrag 2010). Ascending infection of the vagina leads to infection of the chorioamniotic membrane and infection of the amniotic fluid and subsequent transmission to the foetus via the bronchopulmonary tree leading to EOD manifest as respiratory distress and septicaemia. Late onset disease may be caused by nosocomial, horizontal transmission from mother to baby or by transmission through breast milk. In late-onset GBS disease, the GBS bacteria adhere to infant mucosal surfaces, gaining access to the blood stream and crossing the blood brain barrier, leading to meningitis, which is a more common presentation of LOD.

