### 3 Study objectives and endpoints

#### 3.1 Primary objective

To compare the concentrations of IgG specific to the AlpN proteins (RibN, Alp1N, Alp2N and AlpCN) in cord blood from babies, born to women who received the GBS-NN/NN2 vaccine or placebo, according to four vaccination regimens during pregnancy, between the GBS-NN/NN2 and placebo groups:

- Group 1: 2 doses GBS-NN/NN2 at 26 & 30 weeks GA  
(1st dose given 3rd trimester; 4 weeks interval)
- Group 2: 2 doses GBS-NN/NN2 at 22 & 26 weeks GA  
(1st dose given 2nd trimester; 4 weeks interval)
- Group 3: 2 doses GBS-NN/NN2 at 22 & 30 weeks GA  
(1st dose given 2nd trimester; 8 weeks interval)
- Group 4: 1 dose GBS-NN/NN2 at 26 weeks GA  
(one dose given 3rd trimester)
- Group 5: Placebo at 22, 26 and 30 weeks GA  
(1st placebo dose given 2nd trimester, 4 weeks interval)

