#### 3.2 Key secondary objective (safety)

To evaluate the safety and tolerability of the GBS-NN/NN2 vaccine in pregnant women from 22 ( $\pm 1$ ) weeks GA and to evaluate developmental milestones in the baby up to 6 months post-delivery.

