### 3.5 Primary endpoint(s)

The following primary endpoint(s) will be evaluated, by group:

- Concentrations of IgG antibodies specific to the AlpN proteins in cord blood from each baby:
  - The geometric mean antibody concentrations at birth will be calculated
  - The proportions of babies who achieve a concentration of IgG specific to the AlpN proteins above 0.1, 0.2, 0.5, 1, 2, 4 and 8  $\mu\text{g}/\text{mL}$  at birth will be calculated

The primary immunological endpoint analysis will include the values of these endpoints at the time of delivery, anticipated to be approximately 18 weeks (4  $\frac{1}{2}$  months) from administration of the first dose at 22 weeks GA, or 14 weeks (3 $\frac{1}{2}$  months) from administration of the first dose at 26 weeks GA.

If cord blood cannot be obtained, venous infant blood may be collected within 72 hours of birth.

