## 6.4 Reporting of adverse events including SAEs, MAAEs and AESIs

AEs will be reported in the eCRF pages from informed consent until the subject has completed/is withdrawn from the study (including any follow-up period), see details in Table 2 for mothers and Table 3 for babies.

Adverse events identified from the e-diaries will be transferred to the AE form in the eCRF, if they meet the following criteria:

- Any unsolicited AE
- Solicited local or systemic reaction to be assessed for the subject's withdrawal from study or study vaccine
- Solicited local or systemic reaction, rated by the subjects in the eDiary, categorized as severe
- Solicited local or systemic reaction lasting beyond 7 days from the day of vaccination
- Solicited local or systemic reaction that meets the definition of a SAE

Solicited local or systemic reactions are per definition regarded as related to the study vaccine, and the intensity is defined as described in section 6.1.

All maternal SAEs, as well as medically attended adverse events (MAAEs) and AEs of special interest (e.g., GBS disease, autoimmune diseases and immune-mediated reactions) will be reported from the day of signing informed consent for study participation and until the end of the study (Visit 11).

All baby SAEs, as well as MAAEs and AESIs (e.g., GBS disease, abnormal development according to developmental milestones), will be reported from birth up to 180 days post-delivery (Visit 11).

All SAEs, and AESIs, occurring from the time of signing the informed consent form until the subject has completed the study will be reported by completing and sending the SAE form (via email, or if required, via fax) to the pharmacovigilance provider (contact details below) within 24 hours of awareness / learning about the event i.e., within 24 hours after the investigator becomes aware that the event meets the protocol definition of a SAE.

SAEs occurring after study termination must be reported if considered related to the study drug.

After the initial SAE report, the investigator is required, proactively, to provide further information regarding the subject's condition.

In case of a fatal or life-threatening suspected unexpected serious adverse reaction (SUSAR), relevant follow-up information should be forwarded immediately.

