## 7.8 Analysis of immunogenicity (primary endpoint)

The primary objective of the study will be assessed using the following endpoints, based on cord blood from subjects in the BIG set:

- A) IgG antibody concentrations specific to each of the four chosen AlpN proteins
- B) Seroprotection as defined by AlpN-specific IgG concentrations being above the following cut points: 0.1, 0.2, 0.5, 1, 2, 4 and 8 µg/mL

The primary immunological endpoints will be defined as the values of the above parameters obtained in cord blood at the time of delivery (anticipated to be approximately 18 weeks from administration of first vaccine dose, taking place at the pregnancy's 22 weeks gestational age).

The endpoints will be compared, as described below, between the 5 intervention groups:

- Group 1: 2 doses GBS-NN/NN2 at 26 & 30 weeks GA  
(1st dose given 3rd trimester; 4 weeks interval)
- Group 2: 2 doses GBS-NN/NN2 at 22 & 26 weeks GA  
(1st dose given 2nd trimester; 4 weeks interval)
- Group 3: 2 doses GBS-NN/NN2 at 22 & 30 weeks GA  
(1st dose given 2nd trimester; 8 weeks interval)
- Group 4: 1 dose GBS-NN/NN2 at 26 weeks GA  
(one dose given 3rd trimester)
- Group 5: Placebo at 22, 26 & 30 weeks GA  
(1st placebo dose given 2nd trimester, 4 weeks interval)

Comparison between groups 1, 2, 3 and 4 will form the main focus, with group 1 as the perceived standard, whereas groups 2 and 3 each represent useful practical alternatives that are expected to perform on a comparable level, and group 4 as representative for a sub-optimal, but still useful vaccination experience.

**Estimand:** The 'treatment-policy (ITT/effectiveness)' estimand is considered for the primary objective. The estimand is based on data collected in all randomized BIG subjects regardless of the mother's possible discontinuation of trial product or treatment adherence.

**Missing data:** imputation is not envisaged, and data will be analysed as collected. In general, the attrition rate is expected to be low.

The comparison will be conducted as a series of non-inferiority tests, for each choice of antigen (4) and cut-point (7) with two margins:

- binary endpoints (seroprotection): 15% points (0.15) on the absolute scale
- for IgG concentrations: here a GMC ratio of 2/3 is considered adequate.

The null hypotheses for each binary endpoint is:

$$H_0: P_{\text{cut } c, \text{ group } k, \text{ antigen } w} < P_{\text{cut } c, \text{ group } 1, \text{ antigen } w} - 0.15$$

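### The one safety contact for women withdrawn from the study is timed from the last injection, so it may fall 68 to 124 days short of the 180-day infant safety period, and the protocol does not say whether it covers the baby

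*Protocol*

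**What the plan says.** Protocol 4.7.2 limits the contact to "Subjects withdrawn from the study within 6 months after the last product administration" and says that they "will be contacted at least 6 months after the last product administration for recording of SAEs and AEs of special interest". The sentence mentions neither delivery nor the baby, and it leaves out MAAEs.

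The infant commitments are timed from birth:

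- Protocol 3.2, key secondary objective: "to evaluate developmental milestones in the baby up to 6 months post-delivery".
- Protocol 6.4: baby SAEs, MAAEs and AESIs "will be reported from birth up to 180 days post-delivery (Visit 11". Footnote g to Protocol Table 3 gives the same 180-day limit.
- Protocol 6.3: the baby AESIs are GBS disease and abnormal development on the milestone checks.
- Protocol 2.1 describes "late-onset disease (LOD) occurring between day 7 to 89 days of life".

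Protocol 7.6 and SAP 3.5 put into the baby safety set (BSA) every baby whose mother received at least one injection. Protocol 4.7.1 (subject discontinuation), Protocol 4.7.3 (loss to follow-up) and the SAP give no other contact rule for pairs who have left the study.

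**The concern.** Six months after an injection given in mid-pregnancy is much earlier than 6 months after birth. A site can therefore make the contact exactly as written and close the record while the baby is still well inside the period that the safety objective covers. The earlier the last injection, the earlier the permitted contact.

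What is at stake is the completeness of infant safety data. A contact at 8 to 16 weeks of age cannot show a developmental problem that becomes visible at 6 months. For some babies it also comes before the late-onset GBS window has closed. These babies count in the BSA denominator, and SAP 4.7.1 and 4.7.2 present infant events as numbers and percentages. An event after the contact would therefore read as no event.

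**Working it through.** **Inputs**

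- Last injection: 22, 26 or 30 weeks GA. Every group is injected at all three times, as the placebo arm shows: "Group 5: Placebo at 22, 26 and 30 weeks GA" (Protocol 3.1).
- Delivery: "anticipated to be approximately 18 weeks from administration of first vaccine dose, taking place at the pregnancy's 22 weeks gestational age" (Protocol 7.8). Protocol 3.5 counts about 18 weeks "from administration of the first dose at 22 weeks GA, or 14 weeks" from a first dose at 26 weeks.
- Injection windows: first at 21+0 to 23+6 weeks GA, second on Day 26-30, third on Day 54-58 (Protocol Table 2).
- Six months is taken as 182 days. Using 180 or 183 days moves each result by at most 2 days.

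**Reproducing the plan's delivery date.** 22 + 18 = 40 and 26 + 14 = 40 weeks GA. The two statements agree, and birth is placed at 280 days GA.

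**Earliest permitted contact.** Day after birth = (GA at last injection in days) + 182 − 280. Shortfall = 180 − that day.

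| Last injection | Contact, days after birth | Weeks | Shortfall to day 180 |
|---|---|---|---|
| 22 weeks (154 days) | 154 + 182 − 280 = 56 | 8 | 124 |
| 26 weeks (182 days) | 182 + 182 − 280 = 84 | 12 | 96 |
| 30 weeks (210 days) | 210 + 182 − 280 = 112 | 16 | 68 |

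**Visit windows, birth still at 40 weeks**

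- Visit 1 last (GA 147 to 167 days): day 49 to 69.
- Visit 3 last (173 to 197 days): day 75 to 99.
- Visit 5 last (201 to 225 days): day 103 to 127.

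The overall range is about 7 to 18 weeks after birth.

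**Other birth dates (assumed, not in the documents).** Birth at 37 weeks gives days 77, 105 and 133. Birth at 42 weeks gives days 42, 70 and 98. In general the floor reaches day 180 only if birth comes within 182 − 180 = 2 days of the last injection.

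**Late-onset window.** The floor comes before day 89 when birth is more than 182 − 89 = 93 days after the last injection.

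- Last injection at 22+0: births after 154 + 93 = 247 days (35+2). Across the Visit 1 window of 21+0 to 23+6, the threshold runs from 240 days (34+2) to 260 days (37+1). Birth at 40 weeks is beyond it throughout.
- Last injection at 26+0: births after 182 + 93 = 275 days (39+2). At 40+0 the margin is 89 − 84 = 5 days. With birth at 39+1 or earlier, the contact falls on day 90 or later.
- Last injection at 30+0: births after 210 + 93 = 303 days (43+2), so this case is not affected.

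**Women the rule leaves out.** The contact applies only to withdrawal within 6 months of the last injection. On the nominal schedule, a woman who leaves after about day 56, 84 or 112 post-delivery (last injection at 22, 26 or 30 weeks), but before Visit 11 at days 166-194, has no scheduled contact.

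**The case against.** Several points on the other side stand.

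- The 6 months is a minimum. A site that calls at 180 days post-delivery also complies, so the contact can be early but need not be.
- Stopping vaccination is not leaving the study. Protocol 4.7 and 4.7.2 let a woman who stops injections stay for scheduled assessments, and the contact rule does not concern her.
- Protocol 6.4 states the 180-day period for all baby SAEs, MAAEs and AESIs without excepting withdrawn mothers. Protocol 6.2 follows known events to resolution or stability, and inclusion criterion 4 grants access to study-related records. These narrow the gap. They do not close it, because no contact is scheduled that would bring a new late event to light.
- The 6-month milestone endpoint comes from checks at visits. A single contact was not designed to replace them, although abnormal development is an AESI and so within what the contact records.
- Women outside the rule after a 30-week injection are past about day 112, beyond Visit 10 (days 84-96) and the late-onset window.
- Attrition is expected to be low (Protocol 7.8), infant safety is summarised descriptively, and the cord-blood primary endpoint is unaffected.

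A reader might go further and infer that the missed events are concentrated among women who left because of a safety problem. The documents do not show this. Protocol 4.7.1 allows withdrawal for an adverse event, but also for no stated reason. A reader might also infer that GBS disease generally appears after the contact. It does not. Early-onset disease falls in the first 6 days, and Protocol 2.1 cites 205,000 early-onset against 114,000 late-onset cases (205/319, about 64% early). Even day 56 is well into the late-onset window.

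**Conclusion.** The concern holds as a mismatch of time origin and an unclear scope. If sites follow the minimum in Protocol 4.7.2, observation of babies of withdrawn women can end 124, 96 or 68 days before the protocol's own 180-day limit. These figures rest on 6 months being 182 days, birth at 40 weeks GA and nominal injection dates. The shortfall remains under every birth date and visit window examined.

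The late-onset point is firm only for women whose last injection was at Visit 1 and who deliver around term. For a 26-week last injection it is marginal and depends on the date of birth. For a 30-week last injection it does not arise.

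Late infant events can be missed. The documents do not support saying that they will be, or that many women are involved. The gap is small in numbers, but it touches a key secondary safety objective and is cheap to close, so it should be corrected.

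**What to change.** Reconcile Protocol 4.7.2 with Protocol 3.2 and 6.4 in the next amendment:

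- Time the contact at or after 180 days post-delivery, within the Visit 11 window where possible (days 180 to 194).
- Apply it to any woman withdrawn from the study after at least one injection, whenever she left, subject to her consent.
- State that it covers SAEs, MAAEs and AESIs in both mother and baby.

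On the nominal schedule this still satisfies the existing minimum. After a 30-week injection, day 180 post-delivery is 70 + 180 = 250 days after the last dose.

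The cost is a short text change. It is still one contact per woman, but it asks about more (MAAEs, and the baby explicitly) and adds the few women who leave more than 6 months after their last injection. Some women may be harder to reach at the later date.
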